#### **5.4.4. Dose Reductions**

Following dosing interruption or cycle delay due to toxicity, the PF-06840003 dose may need to be reduced when treatment is resumed.

No specific dose adjustments are recommended for Grade 1/2 treatment-related toxicity. However, investigators should always manage their patients according to their medical judgment based on the particular clinical circumstances.

Patients experiencing recurrent and intolerable Grade 2 toxicity may resume dosing at the next lower dose level once recovery to Grade  $\leq 1$  or baseline is achieved.

Dose reductions of PF-06840003 are not allowed for patients receiving the starting dose of 125 mg. Dose reduction of PF-06840003 by 1 and, if needed, 2 dose levels will be allowed depending on the type and severity of toxicity encountered. However, dose reductions below 125 mg daily are never allowed. Patients requiring more than 2 dose reductions will be discontinued from the treatment and entered into the follow-up phase, unless otherwise agreed between the investigator and the sponsor. All dose modifications/adjustments must be clearly documented in the patient's source notes and case report form (CRF).

Once a dose has been reduced for a given patient, all subsequent cycles should be administered at that dose level, unless further dose reduction is required. Dose re-escalation is not allowed.

Patients experiencing a DLT may resume dosing at the next lower dose level (if applicable) once adequate recovery is achieved. Dose reductions for patients experiencing a late onset toxicity or toxicity in the expansion phase will be discussed in consultation with the sponsor.

**Table 3. Dose Modifications for Investigational Product-Related Toxicity**

| Toxicity        | Grade 1                          | Grade 2                          | Grade 3  | Grade 4   |
|-----------------|----------------------------------|----------------------------------|--|---|
| Non-hematologic | Continue at the same dose level. | Continue at the same dose level. | Withhold dose until toxicity is Grade $\leq 1$ , or has returned to baseline, then resume treatment at the same dose level or reduce the dose by 1 level at the discretion of the investigator*. | Withhold dose until toxicity is Grade $\leq 1$ , or has returned to baseline within 14 days, then reduce the dose by 1 level and resume treatment, or discontinue at the discretion of the investigator*. |
| Hematologic     | Continue at the same dose level. | Continue at the same dose level. | Withhold dose until toxicity is Grade $\leq 1$ , or has returned to baseline, then resume treatment at the same dose level**.  | Withhold dose until toxicity is Grade $\leq 1$ , or has returned to baseline, then reduce the dose by 1 level and resume treatment or discontinue at the discretion of the investigator**.                |

\* Nausea, vomiting, or diarrhea must persist at Grade 3 or 4 despite maximal medical therapy to require dose modification.

\*\* Cycle will not be extended to cover for the missing doses.

### 5.5. Investigational Product Storage

The investigator, or an approved representative, eg, pharmacist, will ensure that all investigational products, are stored in a secured area with controlled access under required storage conditions and in accordance with applicable regulatory requirements.

Investigational product should be stored in its original container and in accordance with the label.

Storage conditions stated in the single reference safety document (SRSD) (eg, Investigator Brochure) will be superseded by the storage conditions stated in the labeling.

Site systems must be capable of measuring and documenting (for example, via a log), at a minimum, daily minimum and maximum temperatures for all site storage locations (as applicable, including frozen, refrigerated and/or room temperature products). This should be captured from the time of investigational product receipt throughout the study. Even for continuous monitoring systems, a log or site procedure that ensures active daily evaluation for excursions should be documented. The operation of the temperature monitoring device and storage unit (for example, refrigerator), as applicable, should be regularly inspected to ensure it is maintained in working order.

Any excursions from the product label storage conditions should be reported upon discovery. The site should actively pursue options for returning the product to the storage conditions as described in the labeling, as soon as possible. Deviations from the storage requirements, including any actions taken, must be documented and reported to the sponsor.

Once an excursion is identified, the investigational product must be quarantined and not used until the sponsor provides documentation of permission to use the investigational product. It will not be considered a protocol deviation if the sponsor approves the use of the investigational product after the temperature excursion. Use of the investigational product prior to sponsor approval will be considered a protocol deviation.

Specific details regarding information the site should report for each excursion will be provided to the site.

Site staff will instruct patients on the proper storage requirements for take home study treatment.

## **5.6. Investigational Product Accountability**

The investigative site must maintain adequate records documenting the receipt, use, loss, or other disposition of the investigational product supplies. Patients will be required to return all unused study treatment at the beginning of each cycle.

### **5.6.1. Destruction of Investigational Product Supplies**

The sponsor or designee will provide guidance on the destruction of unused investigational product (eg, at the site). If destruction is authorized to take place at the study site, the investigator must ensure that the materials are destroyed in compliance with applicable environmental regulations, institutional policy, and any special instructions provided by Pfizer, and all destruction must be adequately documented.

CCI [REDACTED]

CCI [REDACTED]

[REDACTED]

[REDACTED]

[REDACTED]

CCI

### **5.7.1. Other Anti-tumor/Anti-cancer or Experimental Drugs**

No additional anti-tumor treatment will be permitted while patients are receiving study treatment. Additionally, the concurrent use of select vitamins or herbal supplements is not permitted.

### **5.7.2. Supportive Care**

Palliative and supportive care for disease related symptoms may be administered at the investigator's discretion and according to any available American Society of Clinical Oncology (ASCO) guidelines.

### **5.7.3. Anti-inflammatory Therapy**

Anti-inflammatory or narcotic analgesic may be offered as needed assuming there is no known or expected drug-drug interaction and assuming the drug is not included in the [Concomitant Treatment\(s\)](#) section.

Due to the immunologic nature of PF-06840003 administration, cerebral edema could theoretically result as a consequence of PF-06840003 administration due to immune infiltration of the brain. Symptoms related to cerebral edema may include headache or neurologic deficit that is either new or worsened. Patients with any signs or symptoms of cerebral edema should be treated as clinically appropriate including initiation or increased systemic corticosteroid dosing, treatment with an osmotic diuretic or surgical decompression. Subsequent PF-06840003 dosing should be immediately interrupted if significant clinical symptoms attributable to cerebral edema develop. Treatment with additional PF-06840003 doses may only be re-initiated if clinically significant symptoms attributable to cerebral edema have resolved to grade  $\leq 1$  or pre-treatment baseline. Patients who develop CTCAE 4.0 grade 4 cerebral edema attributable to PF-06840003 administration should not receive further PF-06840003 doses and should discontinue study therapy.

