**Non-hematologic:**

- Any toxicity attributable to PF-06840003 that results in administration of less than 80% of the planned doses during Cycle 1.
- Grade 4 non hematologic AE.
- Grade 3 AE lasting >7 days despite optimal supportive care.
- Grade 3 CNS AE regardless of duration. CNS AEs are those events listed within the nervous system disorders category in the NCI CTCAE version 4.03.
- Grade 3 QTc prolongation (QTc >500 msec) will be considered a DLT only if persisting after correction of any reversible causes.
- Concurrent aspartate aminotransferase (AST) or alanine aminotransferase (ALT) >3 x upper limit of normal (ULN) and total bilirubin >2 x ULN.

The following AEs will not be considered as DLTs:

- Isolated Grade 3 or 4 laboratory abnormalities that are not associated with clinical sequelae or are corrected to Grade  $\leq$ 1 with supplementation/appropriate management within 72 hours of their onset.

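### After drug-attributed Grade 4 cerebral edema above 125 mg, Protocol Section 5.7.3 rules out further dosing while Table 3 and Section 5.4.4 permit resumption at a lower level, and no visible text says which governs

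*Protocol*

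**What the plan says.** Protocol Section 5.7.3, headed Anti-inflammatory Therapy, describes cerebral edema as a theoretical consequence of the drug's immunologic nature. Its last sentence reads: "Patients who develop CTCAE 4.0 grade 4 cerebral edema attributable to PF-06840003 administration should not receive further PF-06840003 doses and should discontinue study therapy". It mentions no investigator discretion.

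The general dose-modification rules are in Section 5.4. Table 3 covers investigational product-related toxicity. Its Grade 4 non-hematologic cell has the site withhold drug until the event is Grade 1 or lower, or back to baseline "within 14 days, then reduce the dose by 1 level and resume treatment, or discontinue at the discretion of the investigator". The footnote to that row singles out only gastrointestinal events: "Nausea, vomiting, or diarrhea must persist at Grade 3 or 4 despite maximal medical therapy to require dose modification".

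Section 5.4.4 adds a rule for DLTs: "Patients experiencing a DLT may resume dosing at the next lower dose level (if applicable) once adequate recovery is achieved". Section 3.2 lists "Grade 4 non hematologic AE" among the first-cycle events that count as DLTs.

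Section 5.4.4 also sets two limits: "Dose reductions of PF-06840003 are not allowed for patients receiving the starting dose of 125 mg", and "Dose reductions for patients experiencing a late onset toxicity or toxicity in the expansion phase will be discussed in consultation with the sponsor".

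The SAP contains no rule on re-dosing after this event.

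**The concern.** Grade 4 cerebral edema attributed to the drug falls under all three provisions. Section 5.7.3 closes off further dosing. Table 3 makes further dosing a matter of investigator judgment, and for a Cycle 1 DLT Section 5.4.4 allows it. A site managing a Grade 4 toxicity would naturally open the dose-modification section, and nothing there leads to the sentence under Anti-inflammatory Therapy.

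The main stake is patient safety. The severity table in Section 8.8 defines Grade 4 as life-threatening, and the visible text does not settle whether such a patient may be given the drug again. A lesser stake is consistency: treatment duration, relative dose and discontinuations could reflect which provision was followed as well as how the drug was tolerated.

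**Working it through.** No figure in the plan bears on this point, so there is nothing to recompute. The check is to trace the event through each provision.

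**Does the event fall under each rule?**
- Section 5.7.3: yes, by name.
- Table 3: yes. It is product-related, non-hematologic and Grade 4.
- Section 5.4.4, DLT sentence: yes if it occurs in Cycle 1 of Part 1. Section 3.2 confines DLTs to the first 28-day cycle, for the purpose of dose escalation, and sets aside events with a clear alternative explanation. An event attributed to the drug would not ordinarily be set aside on that ground.

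**What does each rule allow?**

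| Situation | Section 5.7.3 | Table 3 | Section 5.4.4 | Conflict? |
|---|---|---|---|---|
| Part 1, Cycle 1, above 125 mg, recovered within 14 days | No further dose | Resume one level lower, or stop, as the investigator judges | May resume one level lower | Yes, with both |
| Part 1, after Cycle 1, above 125 mg, recovered within 14 days | No further dose | As above | Reduction discussed with sponsor | Yes, with Table 3 |
| Part 2, above 125 mg, recovered within 14 days | No further dose | As above | Reduction discussed with sponsor | Yes, with Table 3 |
| Starting dose of 125 mg | No further dose | Lower-dose route closed by Section 5.4.4 | No reduction allowed | No |
| Not recovered | No further dose | Condition for resuming not met | Condition for resuming not met | No |

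One case lies between these rows: a Cycle 1 DLT above 125 mg that recovers after more than 14 days. Table 3's condition is then not met. The DLT sentence sets no time limit of its own, but Section 5.4.3 makes resumption after more than 2 weeks exceptional. It requires obvious clinical benefit and agreement between investigator and sponsor.

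**Is there a link or an order of precedence?** Section 5.4.2 covers interruption for Grade 3 or 4 toxicity. It sends the reader to Section 5.4.3 for the criteria to resume and to the dose-reduction section for the dose. Neither those sections nor Table 3 mentions Section 5.7.3 or cerebral edema. Section 5.7.3 does not mention Section 5.4 or say that it overrides it.

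**Does the ambiguity reach the dose-finding?** Decisions under the modified toxicity probability interval (mTPI) design use the number of patients treated at a dose level and the number of them with a DLT (Table 2; Protocol Section 9.2.1). SAP Section 8.2.4.1 records DLT as a yes/no variable per patient. A patient with a Cycle 1 Grade 4 edema that qualifies as a DLT is counted whether or not dosing later resumes, so neither number changes. The summaries that could change are disposition (SAP Section 8.2.1) and treatment duration and relative dose (SAP Section 8.2.3).

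**The case against.** The strongest reply is that a specific rule narrows a general permission. Table 3 and Section 5.4.4 allow resumption but do not require it, so a site that stops treatment complies with all three provisions. The protocol also keeps other event-specific rules outside Table 3 without a footnote there: QTcF handling is in Section 7.1.5, and withdrawal after a positive pregnancy test is in Section 7.1.1. This is a fair reading and shows that the texts can be reconciled. It does not show that they have been. A site that resumes dosing would follow Table 3 while departing from Section 5.7.3, and it would learn of the departure only by finding a section to which it was not directed.

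Second, a site would not act alone. Section 8.14.1 requires immediate notification of a life-threatening serious event. Section 3.4 triggers a sponsor meeting for events of DLT grade after the DLT window or in Part 2. Section 9.8 describes continuing safety discussions with investigators. This lowers the chance of unnoticed re-dosing but does not tell either party which instruction to apply.

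Third, text before Section 5.7.1 is redacted, and a statement of precedence there cannot be excluded. Even so, the dose-modification sections and Table 3 are visible and contain no pointer to one.

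A reader might infer that every attributable Grade 4 cerebral edema is caught by the conflict. The limits on starting dose, recovery and timing show otherwise. A reader might also size the problem as one patient in a cohort of 2 to 4. That only restates the cohort size: the documents give no event rate, and a share of a cohort does not measure harm from the ambiguity.

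**Conclusion.** The inconsistency is real and stands in the current text, but it is narrow. It exists only above 125 mg and after recovery, within 14 days under Table 3. It is sharpest for Cycle 1 DLTs in Part 1, where both Table 3 and Section 5.4.4 permit what Section 5.7.3 rules out. For late-onset and Part 2 events, Section 5.4.4 calls for sponsor consultation and the conflict is with Table 3 alone.

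Its importance lies in unclear direction on re-exposure after a life-threatening event, which the protocol presents as a theoretical consequence of the drug and not an observed one. It would be tempting to infer that the estimate of the maximum tolerated dose is at risk, or that results will differ systematically by site. The documents support neither: DLT counts and mTPI decisions do not depend on whether the patient resumes, and nothing suggests that several such events are expected. Any effect on exposure and disposition summaries is secondary and cannot be quantified from the documents.

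This conclusion assumes that the redacted text contains no statement of precedence. It takes no position on which clinical rule is right.

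**What to change.** Reconcile Section 5.7.3, Section 5.4.4 and Table 3 so that a single instruction governs Grade 4 cerebral edema attributable to PF-06840003. Then cross-reference that instruction in two places: a footnote to the Grade 4 non-hematologic cell of Table 3, and a clause in the DLT sentence of Section 5.4.4. If Section 5.7.3 is meant as an exception to the general rules, say so there. The content of the rule is for the sponsor's clinical team to decide.

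The cost is one footnote and one clause in the next protocol amendment, plus any wording needed in Section 5.7.3. No patients, visits or procedures are added, and the SAP needs no change.

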### **5.7.4. Surgery**

Caution is advised on theoretical grounds for any surgical procedures during the study. The appropriate interval of time between surgery and PF-06840003 required to minimize the risk of impaired wound healing and bleeding has not been determined. Stopping PF-06840003 is recommended at least 7 days prior to surgery. Postoperatively, the decision to reinitiate

PF-06840003 treatment should be based on a clinical assessment of satisfactory wound healing and recovery from surgery.

## **6. STUDY PROCEDURES**

### **6.1. Screening**

For screening procedures see Schedule of Activities and [ASSESSMENTS](#) section.

### **6.2. Study Period**

For treatment period procedures, see Schedule of Activities and [ASSESSMENTS](#) section.

### **6.3. Follow-up Visit**

For follow-up procedures see Schedule of Activities and [ASSESSMENTS](#) section.

### **6.4. Patient Withdrawal**

Patients may withdraw from treatment at any time at their own request, or they may be withdrawn at the discretion of the investigator or sponsor for safety or behavioral reasons, or the inability of the patient to comply with the protocol-required schedule of study visits or procedures at a given study site.

Reasons for withdrawal of study treatment may include:

- Objective disease progression according to the iRANO criteria. Disease progression is to be confirmed with two consecutive timepoints at least 8 weeks apart in the absence of substantial neurological decline if progression is suspected within 6 months of treatment initiation.
- Global deterioration of health status requiring discontinuation;
- Unacceptable toxicity;
- Pregnancy;
- Significant protocol violation;
- Lost to follow-up;
- Patient refused further treatment;
- Study terminated by sponsor;
- Investigator discretion;
- Death.

Reasons for withdrawal from study follow-up may include:

- Completed study follow-up;
- Study terminated by sponsor;
- Lost to follow-up;
- Refused further follow-up;
- Death.

If a patient does not return for a scheduled visit, every effort should be made to contact the patient. All attempts to contact the patient and information received during contact attempts must be documented in the patient's medical record. In any circumstance, every effort should be made to document patient outcome, if possible. The investigator should inquire about the reason for withdrawal, request that the patient return all unused investigational product, request that the patient return for a final visit, if applicable, and follow-up with the patient regarding any unresolved AEs.

If the patient refuses further visits, no further study specific evaluations should be performed, and no additional data should be collected. The sponsor may retain and continue to use any data collected before such withdrawal of consent.

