19. **Adverse Event (AE) Assessments:** Adverse events should be documented and recorded at each visit using the National Cancer Institute Common Terminology Criteria for Adverse Events (NCI CTCAE) version 4.03. Patients must be followed for AEs for 28 days after the last study treatment administration or until all drug-related toxicities have resolved, whichever is later; or earlier than 28 days should the patient commence another anticancer therapy in the meantime. For serious adverse events (SAEs), the active reporting period to Pfizer or its designated representative begins from the time that the patient provides informed consent, which is obtained prior to the patient's participation in the study, ie, prior to undergoing any study-related procedure and/or receiving investigational product, through and including 28 calendar days after the last administration of the investigational product. SAEs occurring to a patient after the active reporting period has ended should be reported to the sponsor if the investigator becomes aware of them; at a minimum, all SAEs that the investigator believes have at least a reasonable possibility of being related to investigational product are to be reported to the sponsor.
20. **Follow-up:** At least 28 days, and no more than 35 days, after discontinuation of treatment, patients will return to undergo the assessments included in the table above which includes a review of concomitant medications and assessment for resolution of any treatment-related toxicity. Patients continuing to experience toxicity at this point following discontinuation of treatment will continue to be followed at least every 4 weeks until resolution or determination, in the clinical judgment of the investigator, that no further improvement is expected.

**SCHEDULE OF ELECTROCARDIOGRAM, PHARMACOKINETIC AND PHARMACODYNAMIC ASSESSMENTS – FOR COHORTS WHERE INPATIENT EVALUATION IS NOT REQUIRED**

| Protocol Activity  | Screening (≤28 days) | Treatment Period |   |   |   |   |   |       |          |          |          |   |   |   |   |   |         |          |                    |                | End of Treatment |                |   |
|--|----------------------|------------------|---|---|---|---|---|-------|----------|----------|----------|---|---|---|---|---|---------|----------|--------------------|----------------|------------------|----------------|---|

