### **7.1.2. Adverse Events**

Assessment of AEs will include the type, incidence, severity (graded by the NCI CTCAE version 4.03) timing, seriousness, and relatedness. Patients must be followed for AEs for 28 days after the last study treatment administration or until all drug-related toxicities have resolved, whichever is later; or earlier than 28 days should the patient commence another anti-cancer therapy in the meantime.

Adverse events that occur during the study, will be recorded on the AE CRF page.

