### **8.2. Reporting Period**

For SAEs, the active reporting period to Pfizer or its designated representative begins from the time that the patient provides informed consent, which is obtained prior to the patient's participation in the study, ie, prior to undergoing any study-related procedure and/or receiving investigational product, through and including 28 calendar days after the last administration of the investigational product. SAEs occurring to a patient after the active reporting period has ended should be reported to the sponsor if the investigator becomes aware of them; at a minimum, all SAEs that the investigator believes have at least a reasonable possibility of being related to investigational product are to be reported to the sponsor.

AEs (serious and non-serious) should be recorded on the CRF from the time the patient has taken at least 1 dose of investigational product through the patient's last visit.

- If a patient begins a new anticancer therapy, the AE reporting period for non-serious AEs ends at the time the new treatment is started. Death must be reported if it occurs during the SAE reporting period after the last dose of investigational product, irrespective of any intervening treatment.

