### **8.6. Serious Adverse Events**

A serious adverse event is any untoward medical occurrence at any dose that:

- Results in death;
- Is life-threatening (immediate risk of death);
- Requires inpatient hospitalization or prolongation of existing hospitalization;
- Results in persistent or significant disability/incapacity (substantial disruption of the ability to conduct normal life functions);
- Results in congenital anomaly/birth defect;
- Progression of the malignancy under study (including signs and symptoms of progression) should not be reported as an SAE unless the outcome is fatal within the safety reporting period. Hospitalization due to signs and symptoms of disease progression should not be reported as an SAE. If the malignancy has a fatal outcome during the study or within the safety reporting period, then the event leading to death must be recorded as an AE and as an SAE with CTCAE) grade 5 (see the section on [Severity Assessment](#)).

Medical and scientific judgment is exercised in determining whether an event is an important medical event. An important medical event may not be immediately life-threatening and/or result in death or hospitalization. However, if it is determined that the event may jeopardize the patient or may require intervention to prevent one of the other AE outcomes, the important medical event should be reported as serious.

Examples of such events are intensive treatment in an emergency room or at home for allergic bronchospasm; blood dyscrasias or convulsions that do not result in hospitalization; or development of drug dependency or drug abuse.

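### Protocol 6.4 stops all data collection when a patient refuses visits, which conflicts with the 28-day safety follow-up, and no text says which rule prevails

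*Protocol*

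**What the plan says.** Protocol 6.4 distinguishes stopping treatment from leaving follow-up and lists possible reasons for each. For a patient who misses a scheduled visit, the site must try to make contact, ask the reason for withdrawal, invite the patient to a final visit where that applies, and follow up unresolved AEs. The same paragraph adds: "In any circumstance, every effort should be made to document patient outcome, if possible".

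The next paragraph reads: "If the patient refuses further visits, no further study specific evaluations should be performed, and no additional data should be collected". Its closing sentence lets the sponsor keep what was gathered beforehand and describes the event as a withdrawal of consent. Neither list of reasons names withdrawal of consent. The paragraph makes no exception for AEs, SAEs, vital status, telephone contact or medical records.

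Other parts of the protocol set safety duties:

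- Section 7.1.2, repeated in note 19 of the Schedule of Activities: "Patients must be followed for AEs for 28 days after the last study treatment administration or until all drug-related toxicities have resolved", whichever is later. The only early end stated is the start of another anticancer therapy.
- Schedule of Activities, note 20: "At least 28 days, and no more than 35 days, after discontinuation of treatment, patients will return to undergo the assessments". This is the one routinely scheduled visit after End of Treatment.
- Section 8.2: SAEs are reportable through 28 calendar days after the last dose, and "Death must be reported if it occurs during the SAE reporting period after the last dose of investigational product, irrespective of any intervening treatment". AE entry on the case report form (CRF) runs to the patient's last visit.
- Section 8.6: if the malignancy proves fatal during the study or the safety reporting period, "the event leading to death must be recorded as an AE and as an SAE".

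**The concern.** Refusing to travel to a clinic is not the same as refusing all contact. Patients with recurrent glioma who come off treatment may well be unable or unwilling to attend but content to take a call or have their records read. Section 6.4 has no category for them. Read as written, it handles them as if consent had been withdrawn and ends all collection, while other sections say follow-up must continue. A site cannot satisfy both instructions and is not told which to follow.

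Safety is a primary endpoint in both parts. SAP 7.1 analyses safety data as observed, without imputation, so events not collected after refusal simply drop out of the summaries. Deaths also count as events in the exploratory progression-free survival analysis (SAP 8.2.5.2).

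**Working it through.** The plan states no figure on this point. The check compares the texts and then sets out what scale can be shown.

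**1. What triggers the stop.** The condition in 6.4 is refusal of further visits. The reference to withdrawal of consent that follows has no other antecedent in the section, so refusal of visits alone triggers the full stop.

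**2. Which duties it meets.**

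| Duty | Source | Exception for refused visits? | Result |
|---|---|---|---|
| AE follow-up, 28 days or to resolution | 7.1.2; Schedule note 19 | None | Direct conflict |
| SAE and death reporting, 28 days | 8.2; 8.6 | None | Ambiguous: 6.4 bars collecting data, 8.2 still requires reporting |
| Outcome in any circumstance | 6.4 | None, but softened by its closing qualifier | Milder conflict |
| AE entry on the CRF | 8.2 | Ends at the last visit | No conflict with 6.4, but shorter than 7.1.2 for a refuser |

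Patients who merely miss visits are not affected, because 6.4 requires contact with them and follow-up of unresolved AEs.

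**3. How much time is lost.** The gap runs from the last attended visit to at least 28 days after the last dose. The Schedule has an End of Treatment visit with AE assessment, vital signs and laboratory tests, so a patient who attends it and declines only the 28-35 day visit is covered to that point. The timing of End of Treatment relative to the last dose is not given, so the number of days lost cannot be fixed.

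**4. Scale in Part 2.** One patient whose first event of a given type follows refusal changes its observed incidence by 1/20 = 5 points at n=20, or 1/25 = 4 points at n=25.

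The refusal rate is an assumption. Take an event confined to the unobserved period, with true rate p, and let k of 20 patients be unobserved there. The chance of seeing at least one case is 1 − (1 − p)^(20 − k).

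| p (assumed) | k = 0 | k = 2 | k = 4 |
|---|---|---|---|
| 10% | 87.8% | 85.0% | 81.5% |
| 5% | 64.2% | 60.3% | 56.0% |

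**5. Could it touch a DLT?** Among the criteria in section 3.2 is "Grade 3 AE lasting >7 days despite optimal supportive care", which needs follow-up to classify. The exposed case is narrow:

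- The 80% dose mark is 0.80 × 28 = 22.4, so 23 once-daily doses (Day 23). Twice daily it is 0.80 × 56 = 44.8, so 45 doses (morning of Day 23). Both assume no missed dose.
- With dosing stopped at onset, a once-daily patient has taken 22/28 = 78.6% for onset on Day 23 and 23/28 = 82.1% for onset on Day 24. From Day 24 neither the replacement rule (3.1.1) nor the DLT criterion for receiving under 80% of doses applies.
- Onset on Days 24-28 puts the eighth day on Days 31-35, after Cycle 1. That is 5 of 28 cycle days (17.9%), a share of the calendar and not a probability.
- The event must also be outside the nervous system, since "Grade 3 CNS AE regardless of duration" is a DLT in itself. Refusal must come before a recovery assessment (5.4.2) or unplanned visit has settled the duration.

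If a DLT were lost this way in a cohort of four, Table 2 would read 0/4 (Escalate) instead of 1/4 (Stay). That is true of any single lost DLT and says nothing about how likely this route is.

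**The case against.** The strongest reply is that the paragraph sets its own scope. It speaks of withdrawn consent, and a specific rule for that situation properly limits general follow-up rules. The lists of reasons are open-ended, so the absence of withdrawal of consent from them shows little. The consent document was not available for this review and might define degrees of withdrawal. Read in order, 6.4 also asks about unresolved AEs before the stop takes effect. This is a plausible account of intent, but the written trigger is still refusal of visits, and sites act on the written trigger. If the intent was narrower, the fix writes it down.

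Three stronger conclusions that a reader might draw are not supported:

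- **That declining the follow-up visit leaves all 28 post-dose days without data.** The End of Treatment visit carries an AE assessment. The whole window is lost only if that visit is also missed or falls on the last dosing day.
- **That SAE and death reporting is barred.** Nothing in 8.2 or 8.14.1 exempts these patients. Section 8.14.1 obliges the investigator to pursue information on every SAE, and 8.2 covers later SAEs that come to the investigator's notice. A site could reasonably keep reporting. The texts conflict; they do not clearly prohibit it.
- **That dose decisions are at risk in practice.** The DLT route is a chain of unlikely conditions. Section 3.1.1 holds the next cohort until every patient has completed 28 days of evaluation or had a DLT, so a refusal before Day 28 would be visible. Section 9.8 provides for ongoing discussion of AEs at each dose level between investigators and sponsor. SAP 5.7 leaves room for medical review of other major deviations.

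**Conclusion.** The conflict is real and should be corrected. Section 6.4 ends data collection on refusal of visits, sections 7.1.2, 8.2 and 8.6 require safety information without an exception for refusal, and no text gives precedence. The practical loss is AEs, toxicity resolution and vital status after the last attended visit, in patients who would have accepted less burdensome contact. For SAEs and deaths the effect is uncertainty about the duty.

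The size cannot be derived because the documents give no refusal rate. Each affected Part 2 patient can move an incidence by 4 to 5 points, and the detection figures above rest on assumed event and refusal rates. No primary analysis or dose decision is shown to change. The conclusion assumes that some patients refuse visits without withdrawing consent and that the consent document does not already resolve the matter.

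**What to change.** Amend Protocol 6.4 to separate the two situations:

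- **Explicit withdrawal of consent:** keep the full stop on new data collection.
- **Refusal of visits alone, where consent allows:** collect AEs, SAEs, the resolution date of any ongoing toxicity (with routine-care laboratory results where available), new anticancer therapy and vital status, by telephone or from medical records, through at least 28 days after the last dose.

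In 8.2, align the wording that ends AE recording at the last visit, so that for these patients it runs to the same point.

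The cost is a protocol amendment, possibly a change to the consent wording, and a call or record review by existing site staff. No visit or procedure is added. One limit remains: a call cannot establish how long Grade 4 neutropenia lasted, so that DLT criterion would still depend on blood counts taken in routine care.
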